#### **7.7.2. Serious Adverse Events**

Summaries of incidence rates and relationship to the study product/procedure of individual SAEs will be prepared. Summaries will provide both the number of patients and the number of events within a reporting period. Percentages provided will be the percent of patients experiencing one or more serious adverse events. A data listing of SAEs will also be provided, displaying details of the event(s) captured on the CRF.

#### **7.7.3. Adverse Events of Interest**

Summaries of incidence rates of the following AEs by treatment group will be prepared:

- Infection of wound and/or area surrounding wound
- Amputation of lower extremity
- Allergic reaction
- Excessive redness, pain, swelling or blistering of wound

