### **6. ADVERSE EVENT**

#### **6.1. Principal Investigator Responsibilities**

The investigator (or designee) should record and maintain all adverse events that occur over the course of the patient's participation in the study (randomization through study exit) during or outside of study visits. Adverse events that are reported to the sponsor will be assessed by an investigator. Adverse event assessments should include severity, seriousness, and relatedness to the product, study procedures and pre-existing conditions. See Section 6.4 for adverse events that are required to be reported to the Sponsor.

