#### **6.4. Adverse Event Reporting**

The following adverse events are required to be promptly reported to the sponsor on the adverse event CRF:

- Any serious adverse event whether or not it is related to a study product/procedure

- Any adverse event that in the opinion of the investigator is definitely related, probably related, or possibly related to a study product and/or study procedure
- The following adverse events whether or not they are related to a study product/procedure:
  - Infection of wound and/or area surrounding wound
  - Complete or partial amputation of lower extremity
  - Allergic reaction

Serious adverse product effects should be reported to the sponsor as soon as possible. Pre-existing conditions or adverse events that occur prior to randomization are not required to be reported.

The investigator (or designee) is also required to report AEs to the IRB/EC if the AEs are required to be reported per the IRB/EC reporting requirements.

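### The fourth adverse event of interest is not on the list of events reported regardless of relatedness, so its rate by arm may be incomplete and could be captured unequally

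*Combined protocol and SAP*

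**What the plan says.** Section 7.7.3 states: "Summaries of incidence rates of the following AEs by treatment group will be prepared". It then names wound infection, lower-extremity amputation, allergic reaction and "Excessive redness, pain, swelling or blistering of wound".

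Section 6.4 sets the route to the sponsor: "The following adverse events are required to be promptly reported to the sponsor on the adverse event CRF". It gives three categories:

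- The first is by seriousness: "Any serious adverse event whether or not it is related to a study product/procedure".
- The second is by the investigator's judgment of relatedness: "Any adverse event that in the opinion of the investigator is definitely related, probably related, or possibly related to a study product", extended to study procedures.
- The third is by name: "The following adverse events whether or not they are related to a study product/procedure", followed by wound infection, amputation and allergic reaction only.

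Section 6.1 is wider at site level: the investigator "should record and maintain all adverse events that occur over the course of" the patient's participation. It then points elsewhere for the sponsor's share: "See Section 6.4 for adverse events that are required to be reported to the Sponsor". Section 6.3 makes assessment of severity, seriousness and relatedness mandatory for events that must be reported to the sponsor. Section 7.7.1 plans summaries of individual events and a listing of all of them, with severity, seriousness and relationship.

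Sections 3 and 5.7 blind the subject only. No blinded assessor of relatedness is named.

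**The concern.** The sponsor chose four events for a by-arm display, but the reporting rule removes the relatedness filter from only three. For the fourth, a non-serious case is required on the CRF only after someone who is not described as blinded has judged it at least possibly related. Patients in the matrix arm can qualify through the product or a procedure. Control patients can qualify only through a procedure. An event count that depends on that judgment may fall short of the true count, and the shortfall could differ between arms.

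At stake is one line of the safety table. It could understate local wound reactions in both arms, or show a difference that comes from reporting rather than from treatment. Analysis cannot recover events that were never entered.

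**Working it through.** The plan states no figure to reproduce. The check is a comparison of the two lists, a trace of one case, and an illustration of size.

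**1. The lists side by side**

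| Event of interest (7.7.3) | On the CRF whether or not related (6.4)? |
|---|---|
| Wound infection | Yes |
| Amputation | Yes |
| Allergic reaction | Yes |
| Redness, pain, swelling or blistering | No: only if serious or at least possibly related |

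Three of four match.

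**2. Trace of a non-serious local reaction judged unrelated**

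- Section 6.1: recorded at site.
- Section 6.4: meets none of the three categories, so no CRF report is required.
- Section 6.3: no assessment of severity or relatedness is mandatory.
- Sections 7.7.1 and 7.7.3: expected in the listing and in the by-arm summary. No section says how it gets there.

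No other scheduled item is a clear substitute. The follow-up list in Section 5.12 names observation for infection. Appendix A places the pain scale at Week 0 and again at closure or Week 12. Photographs are taken, but no plan derives this event from them.

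**3. Illustration of size**

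Inputs: 24 patients per arm (Section 3). The true rate p, equal in both arms, and the capture probabilities c_T (matrix) and c_C (control) are assumptions; the documents give none of them.

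Observed rate = p × c. False difference = p × (c_T − c_C). Expected count per arm = 24 × p × c.

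| Capture, matrix vs control | p = 10% | p = 20% | p = 30% |
|---|---|---|---|
| 60% vs 60% | 6% vs 6%: 0 points | 12% vs 12%: 0 | 18% vs 18%: 0 |
| 100% vs 80% | 10% vs 8%: 2 | 20% vs 16%: 4 | 30% vs 24%: 6 |
| 90% vs 50% | 9% vs 5%: 4 | 18% vs 10%: 8 | 27% vs 15%: 12 |
| 80% vs 20% | 8% vs 2%: 6 | 16% vs 4%: 12 | 24% vs 6%: 18 |

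The largest entry is 0.30 × (0.80 − 0.20) = 0.18, or 24 × 0.24 = 5.8 against 24 × 0.06 = 1.4 expected patients, when the true value is 24 × 0.30 = 7.2 in each arm.

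With equal 60% capture there is no false difference, but the expected counts are 1.4, 2.9 and 4.3 per arm against true values of 2.4, 4.8 and 7.2. Incomplete capture alone does not make the comparison differential.

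The unequal rows all assume better capture in the matrix arm. The documents do not fix that direction, and swapping c_T and c_C reverses the sign.

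**The case against.** A reader might infer that this event is captured only when serious or judged related, and that its rate will certainly be incomplete and biased between arms. The documents do not support that reading, for four reasons.

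- Section 6.1 has sites record every adverse event from randomization to exit. Appendix A schedules adverse events through the treatment visits and at the two-week follow-up. Section 7.7.1 plans a full listing. Section 6.4 can be read as a rule for prompt reporting rather than a limit on collection.
- The filter in Section 6.4 covers study procedures and is set as low as possibly related. Controls also undergo debridement, cleansing and dressing, so their local reactions can qualify.
- Some such reactions would be entered as infection or allergic reaction, which are reportable in any case.
- Adverse event incidence is a tertiary outcome. Section 7.6.3 makes tertiary endpoints exploratory, with testing only on request, and no decision rule in the plan is tied to this line.

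All four stand as limits on the strength of the claim. They do not close the gap. Section 6.1 itself separates recording from reporting, Section 6.4 names the adverse event CRF as the route, and Section 6.3 makes assessment mandatory only for reportable events. The affected cases are non-serious local reactions judged unrelated to product and procedure and not classed as infection or allergy. For these, Section 6.4 can be followed to the letter and the Section 7.7.3 summary still be undercounted.

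**Conclusion.** The mismatch between Sections 6.4 and 7.7.3 is established from the text. Its effect is a risk, not a certainty: the by-arm rate of the fourth event may be incomplete, and could be differential because only one arm receives the study product and the investigator who assesses relatedness is not described as blinded. The size is unknown. Under the assumed true rates and capture probabilities, the false difference lies between 0 and 18 points, and no single scenario in that range should be quoted as the expected effect. The conclusion rests on the plan's silence about whether recorded, non-reportable events enter the analysis database; if they all do, with relatedness and severity assessed, the problem disappears. The primary endpoint is not affected. The point is worth acting on because the correction is small.

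**What to change.** Add the fourth event, worded as in Section 7.7.3, to the Section 6.4 list of events reported whether or not related. All four events of interest then have the same CRF requirement in both arms, and the relatedness filter no longer decides which cases of this event must be reported. In the illustration, required capture becomes 100% in each arm and the false difference 0.

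Alternatively, state that every adverse event recorded under Section 6.1 is entered on the CRF, and widen Section 6.3 so that severity and relatedness are assessed for all of them. That also supplies the data which Section 7.7.1 expects.

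Either way, define what counts as excessive. The term is undefined, so the threshold would otherwise still rest on the judgment of investigators not described as blinded, and balanced capture would not be assured.

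The cost is one line of text and a few more CRF entries. Patients already attend weekly and adverse events are already on the visit schedule, so no visit is added.

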### **7.8. Strategies to Address Missing Data**

Patients who are missing complete wound closure will be considered as “missing data patients”. Missing complete wound closure status will be imputed using a logistic regression multiple imputation approach for dichotomous outcome data. In this approach, missing healing status will be imputed from logistic regression models with independent variables of age, gender, and other variables to be specified in the formal statistical analysis plan. This will be performed 50 times in each arm in order to generate 50 “complete” datasets. The one-sided Farrington & Manning test for assessing treatment difference will be carried out on each of the 50 complete datasets, with the results being combined across the 50 complete datasets using standard multiple imputation theory to obtain one overall p-value

comparing the two treatments on the primary endpoint after accounting for missing data.

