#### **Primary Outcome Measures:**

- Complete re-epithelialization of wound as assessed by the evaluator within 12 weeks after the initial application of the study product plus confirmation of no drainage or need for additional dressing 2 weeks after complete re-epithelialization.

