### **5.13.2. Patient Withdrawal**

A patient (or patient's LAR) may choose to withdraw from the study at any time without penalty or loss of benefits. The patient should notify the investigator (or designee) of his/her desire to withdraw, and the investigator (or designee) should ask for and document the reason for withdrawal. The investigator may also choose to withdraw a patient from the study at any time if he/she considers it to be in the patient's best interest. The reason for withdrawal should be recorded. Any data collected on the patient up to the point of withdrawal may be used in the study.

If complete wound closure has not been confirmed at the time of withdrawal from the study, then the investigator should attempt to

determine the status of the wound at the time of the patient's withdrawal to the best of the patient's ability (i.e., healed, not healed, seeking additional treatment, not seeking additional treatment) and to complete as many of the patient-reported outcomes questionnaires as the patient is able and willing to complete.

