## 7. STATISTICAL CONSIDERATION

### 7.1. Hypotheses to be Tested

#### 7.1.1. Primary Endpoints:

The null hypothesis ( $H_0$ ) for the primary endpoint is that the difference in proportion of patients achieving 100% re-epithelialization by week 12 between the synthetic hybrid-scale fiber matrix group ( $\pi_1$ ) and the control group ( $\pi_2$ ) is less than or equal to the superiority margin of +0.10 based on a one-sided Farrington & Manning test. The alternative hypothesis ( $H_1$ ) is that the difference is less than the superiority margin of +0.10. These can be seen in the equations below:

$$H_0: \pi_1 - \pi_2 \geq +0.10$$

$$H_1: \pi_1 - \pi_2 < +0.10$$

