## **7.6. Study Outcome**

### **7.6.1. Primary Endpoints**

100% re-epithelialization will be assessed every week for 12 weeks or until 100% re-epithelialization, whichever occurs first. Persistence of wound closure will be verified via confirmatory visit within 2 weeks after complete closure has been first determined.

For the primary endpoint of 100% re-epithelialization at week 12 a two-stage analysis will test first if the rate of 100% re-epithelialization is superior between groups using a chi squared and/or Farrington & Manning test. Superiority for synthetic hybrid-scale fiber matrix will be demonstrated if the lower bound of the 90% CI of the difference in proportions lies above the superiority margin of +10%.

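### A wound recorded as closed but never confirmed at 2 weeks appears to count as an observed success, because the test and the missing-data rule omit the confirmation that the declared primary outcome requires

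*Combined protocol and SAP*

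**What the plan says.** The primary outcome in Section 3 has two parts: evaluator-assessed re-epithelialization within 12 weeks, "plus confirmation of no drainage or need for additional dressing 2 weeks after complete re-epithelialization". Section 1 gives the same two parts.

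The statistical sections use only the first part. The hypothesis in Section 7.1.1 concerns the "proportion of patients achieving 100% re-epithelialization by week 12". The test in Section 7.6.1 is introduced with "For the primary endpoint of 100% re-epithelialization at week 12". Section 7.6.1 also says "Persistence of wound closure will be verified via confirmatory visit within 2 weeks after complete closure has been first determined", but attaches no scoring consequence to a visit that does not take place.

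Section 7.8 opens its definition of missing data with "Patients who are missing complete wound closure will be considered as", and continues: "Missing complete wound closure status will be imputed using a logistic regression multiple imputation approach for dichotomous outcome data". It does not mention the confirmation visit. What it defers to a formal SAP is the choice of further imputation covariates, not the definition of who is missing.

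Section 5.13.2 foresees the situation: "If complete wound closure has not been confirmed at the time of withdrawal from the study", the investigator should try to "determine the status of the wound at the time of the patient's withdrawal to the best of the patient's ability". Healed is one of the listed answers. The section does not say whether that answer enters the primary analysis.

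**The concern.** Take a patient whose wound the evaluator records as closed at week 8 and who withdraws or is lost before the confirmation visit. Closure is on record, so on its face Section 7.8 has nothing to impute. Sections 7.1.1 and 7.6.1 ask only about re-epithelialization, so the patient enters as an observed success. The second half of the declared outcome was never seen.

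Only patients who close can arrive here, so the path is fuller in the arm with more closures. Counting these patients as successes tends to favour Restrata, and counting them as failures costs Restrata more. With 48 patients and a 10-point margin, one or two classifications can decide the result.

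Timing matters too. Only the subject is masked (Section 3), and the unblinded interim assessment of this endpoint is reported to a Sponsor group (Section 7.4). A rule settled late could be settled with its effect in view. The interim conditional power would carry the same ambiguity.

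**Working it through.** **1. The same patient under each section (evaluator-recorded closure, no confirmation result)**

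- Sections 1 and 3: the declared outcome is not shown to be met.
- Sections 7.1.1 and 7.6.1: re-epithelialized by week 12, hence a success.
- Section 7.8, plain wording: closure is not missing, hence not imputed.
- Section 7.8, if complete wound closure is taken to mean confirmed closure: missing, hence imputed.
- Section 7.2, per-protocol set: requires primary-endpoint data, without saying whether that includes the confirmation.

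No section chooses among these.

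**2. The plan's own figure**

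Inputs from Section 7.3: 80% versus 40%, margin 0.10, one-sided alpha 0.05, 20 per group for power 0.80, and 48 in total after 20% loss. The direction of the test is taken from the success rule in Section 7.6.1.

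Farrington-Manning power = Φ{[(p1 − p2 − 0.10)√n − 1.645·s0]/s1}. The restricted rates are 0.657 and 0.557, so s0 = √(0.657×0.343 + 0.557×0.443) = 0.687, and s1 = √(0.8×0.2 + 0.4×0.6) = 0.632. At n = 20 this gives Φ{(1.342 − 1.130)/0.632} = 0.63 (exact 0.65). The stated 0.80 is not reproduced; the formula needs 31 per group. That is a separate matter, on which this point does not depend. The baseline used below is exact power at 24 per group, 0.729.

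**3. How many patients could be affected**

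The documents give no rate of missed confirmations. If the plan's 20% loss is assumed to fall at a constant rate over 12 or 14 weeks, the share of closers lost in a 2-week gap is 1 − 0.8^(2/12) = 3.7% or 1 − 0.8^(2/14) = 3.1%.

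At 3%, the expected counts are 24 × 0.8 × 0.03 = 0.58 Restrata and 24 × 0.4 × 0.03 = 0.29 control patients, a 2:1 ratio. The chance that neither arm has one is [(1 − 0.024)(1 − 0.012)]^24 = 0.42.

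**4. All-success against all-failure scoring**

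Exact Farrington-Manning power at 24 per group, all patients otherwise observed. The verdict changes come from 200,000 simulated trials with the same patients scored both ways.

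| Share of closures unconfirmed (assumed) | Rates if scored as failures | Difference | Exact power | Verdict changes |
|---|---|---|---|---|
| 0 | 80.0% vs 40.0% | 40.0 points | 0.729 | – |
| 3% | 77.6% vs 38.8% | 38.8 points | 0.684 | 7.8% |
| 5% | 76.0% vs 38.0% | 38.0 points | 0.654 | 11.7% |
| 10% | 72.0% vs 36.0% | 36.0 points | 0.578 | 19.8% |

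Most changes run from pass to fail: roughly 6 of the 8 percentage points at 3%, and 17 of the 20 at 10%.

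**5. Individual patients (one-sided p against the 10-point margin)**

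- 20 per group: 16 vs 8 closures gives p = 0.025; 15 vs 8 gives 0.054.
- 24 per group: 19 vs 10 gives 0.025; 18 vs 10 gives 0.049; 17 vs 10 gives 0.089.

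Near the planned rates, rescoring one Restrata closure crosses 0.05 at 20 per group. At 24 per group it takes two.

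**The case against.** The strongest reply is that Section 7.8 may already cover the case. Section 5.13.2 speaks of closure that has not been confirmed, which suggests that complete wound closure is a status needing confirmation. Section 7.8 also ends by comparing the arms on the primary endpoint. On that reading the patient is missing and is imputed. This is a fair reading, but it is nowhere stated, and Sections 7.1.1 and 7.6.1 point the other way. It makes the problem an unresolved wording rather than a proven misanalysis.

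A second reply is that the real fault lies upstream, in the difference between the declared and the tested endpoint. That is largely right. Harmonising the endpoint removes most of the problem, but Section 7.8 would still need to say what happens when only the confirmation is absent.

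A third is that few patients are involved. Under the 3% assumption fewer than one is expected in total. Section 5.13.3 requires repeated contact attempts and does not exit a patient for a missed visit, which makes the path rarer. This limits the size of the point without removing it.

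Three stronger readings are tempting, and the documents do not support them:

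- A reader might infer that one section expressly calls this patient a failure. None does; that status only follows from the unmet two-part outcome.
- A reader might infer that the plan counts a patient-reported healed status at withdrawal as a success. Section 3 requires assessment by the evaluator, so such a patient can be read as missing closure and already imputed. What is absent is an explicit statement.
- A reader might infer that Section 5.13.1 has no exit route for these patients. It does: withdrawal and loss to follow-up are both listed.

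**Conclusion.** The point holds as a conflict between the declared outcome and the rules that score it. On plain wording, an evaluator-closed but unconfirmed patient is analysed as an observed success on an outcome not shown to have occurred. It should be corrected, with medium confidence as to its practical effect.

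The size is an outer bound: power 0.73 against 0.68 and a different verdict in about 8% of trials at a 3% share, or 0.58 and about 20% at a 10% share. The 3% comes from spreading the plan's 20% loss evenly over time; the 10% has no basis in the documents. A reader might take these figures as the effect of the correction proposed here. They are not: they contrast all-success with all-failure scoring, and imputation would probably leave many of these patients as successes. They also treat all 24 patients per group as otherwise observed, so loss before closure is not included.

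**What to change.** Use one endpoint, confirmed closure, in Sections 1, 3, 7.1.1, 7.6.1 and 7.8, and define missingness in Section 7.8 on that endpoint:

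- Score observed non-closers as non-successes, with no imputation.
- Treat evaluator-closed patients with no confirmation result as missing the confirmation component. Impute it within the existing 50 datasets from a model fitted among closers only, pooled over arms with treatment as a covariate if numbers are small. At the planned rates about 19 + 10 closers are expected in 24 per group, so pooling is likely to be needed.
- Do not put recorded closure into the full logistic model as a predictor. Every non-closer is a certain non-success, so the model would suffer separation, more so if fitted by arm.
- State that a patient-reported healed status under Section 5.13.2 is not evaluator-assessed closure and is handled as missing.
- Add one sensitivity analysis that scores all closed-but-unconfirmed and healed-at-withdrawal patients as not closed, and report their number by arm.

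The cost is wording and one extra analysis, with no new visits or data. The Restrata closure rate may become slightly less favourable. The wording should be fixed before the interim assessment, which uses the same endpoint.

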## **5.13. Study Exits**

### **5.13.1. Study Participation Exit Points**

A patient's participation in the study will end after any of the following:

- Patients with complete re-epithelialization and closure confirmation
- Patients without complete re-epithelialization at 12 weeks
- Patient withdrawal
- Patient lost to follow-up
- Amputation of all or part of the study limb
- Closure of study
- Patient death

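### Section 7.8 imputes closure whatever the reason for exit, so a patient who died or lost the ulcer to amputation can be counted as healed; the bias can go either way

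*Combined protocol and SAP*

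**What the plan says.** The primary endpoint (section 3) is "Complete re-epithelialization of wound as assessed by the evaluator within 12 weeks after the initial application of the study product", followed by a confirmation two weeks later.

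Section 5.13.1 lists the events that end participation. They include death, withdrawal, loss to follow-up and "Amputation of all or part of the study limb". They also include "Patients without complete re-epithelialization at 12 weeks", but those patients have an observed failure and are not missing.

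For withdrawals without confirmed closure, section 5.13.2 asks the investigator to try to establish the wound's status: "healed, not healed, seeking additional treatment, not seeking additional treatment".

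Section 7.2 makes mITT the primary efficacy population. It requires at least one application but not an observed outcome.

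Section 7.8 begins "Patients who are missing complete wound closure will be considered as" missing-data patients, then states: "Missing complete wound closure status will be imputed using a logistic regression multiple imputation approach for dichotomous outcome data". The model uses "independent variables of age, gender, and other variables to be specified in the formal statistical analysis plan". On the number of imputations it says "This will be performed 50 times in each arm in order to generate 50" completed datasets. The Farrington & Manning test is applied to each dataset and the results are pooled.

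**The concern.** Section 7.8 sorts patients only by whether closure status is missing, not by why. Death before closure rules the endpoint out, and so does an amputation that removes the study ulcer. Both end participation, so neither patient reaches a 12-week assessment, and no section codes either as a failure. Followed as written, the plan gives such a patient a probability of closure drawn from patients who stayed under observation.

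Amputation is foreseen: it is reportable under 6.4 and an event of interest under 7.7.3. With 24 patients per arm, a few such exits can move the primary difference by several points. The interim conditional power in 7.4 uses the same endpoint and would carry the same error.

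The wound status collected under 5.13.2 raises a related gap. The plan does not say whether a recorded unhealed wound is an outcome, a predictor in the imputation model, or neither. That choice could be made after the data are seen.

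**Working it through.** **Inputs.** From section 7.3: closure 80% Restrata and 40% control, margin +10 points, one-sided alpha 0.05. From section 3: 24 per arm. From 7.8: 50 imputations in each arm, read here as arm-specific models because no treatment term is named. Numbers of deaths, amputations or unhealed exits are assumptions; the documents give none.

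**The plan's own figure.** Section 7.8 contains none to reproduce. The 20 per group in 7.3 does not reproduce from its stated inputs (Farrington & Manning gives 31 per arm), but nothing below depends on it.

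**Step 1: shift in the difference.** Let kR and kC be exits that should count as not closed but are imputed at the arm's observed rate.

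Shift = (0.8 × kR − 0.4 × kC) / 24

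| kR | kC | Shift (points) |
|---|---|---|
| 1 | 1 | +1.7 |
| 2 | 2 | +3.3 |
| 4 | 4 | +6.7 |
| 1 | 2 | 0.0 |
| 1 | 3 | −1.7 |
| 0 | 4 | −6.7 |

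The shift is zero at kC = 2 × kR. Below that ratio of control to Restrata exits it favours Restrata; above it, control.

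**Step 2: four exits per arm.** Observed closures are 16/20 and 8/20.
- Counted as not closed: 16/24 − 8/24 = 33.3 points. The restricted estimates under the +0.10 margin are 0.55 and 0.45, so SE = √[(0.55 × 0.45 + 0.45 × 0.55)/24] = 0.1436. Then z = (0.3333 − 0.10)/0.1436 = 1.62, one-sided p = 0.052.
- Imputed, in expectation: 16/20 − 8/20 = 40.0 points.

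**Step 3: rejection rate on the margin.** The true rates, with exits counted as not closed, are 50% and 40%. Each patient in an affected arm has a 10% chance of such an exit, so closure among those who stay is 0.50/0.90 = 55.6% (Restrata) or 0.40/0.90 = 44.4% (control). Imputation was by arm without covariates, 50 times, pooled by Rubin's rules with the Farrington & Manning variance. The comparator uses the same test.

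| Exits | Expected imputed difference | Rejection, imputed | Rejection, counted as not closed |
|---|---|---|---|
| 10% Restrata only | 55.6 − 40.0 = 15.6 | about 10–11% | about 5% |
| 10% both arms | 55.6 − 44.4 = 11.1 | about 6% | about 5% |
| 10% control only | 50.0 − 44.4 = 5.6 | about 3% | about 5% |

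**Step 4: exits that follow failure to heal.** At 80% and 40% closure there are 4.8 and 14.4 non-closers. If half of each leave early, 2.4 and 7.2 are missing. Imputed rates are 19.2/21.6 = 88.9% and 9.6/16.8 = 57.1%, a difference of 31.7 points against a true 40.0. In simulation, the chance of success falls from 72% (exits counted as not closed) to 45% (imputed).

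**The case against.** The strongest reply is that the plan is silent rather than wrong. A recorded unhealed status may be read as not missing, since 7.8 does not define missing closure. Section 5.13.2 allows data collected up to withdrawal to be used. The covariate list is left open, so wound area or status could still enter the model. This stands for withdrawals: a reader might infer that the plan collects this status and discards it, but the documents do not say so. It does not answer the case of death or amputation. Extra covariates change the imputed probability; they do not make closure impossible.

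A reader might also infer that every exit with an unhealed wound is a known failure. The endpoint window is 12 weeks, and mean time to closure in the pilot was 6.4 weeks (section 2.1), so a patient unhealed at week 3 has an unknown 12-week outcome. That exit is a likely failure, and how to count it is a choice of estimand.

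The exclusions for osteomyelitis or exposed bone, active infection and life expectancy under six months (4.2) make the clearest failures less likely. This is fair, and it limits the expected number of such exits.

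**Conclusion.** The point holds. Applied literally, 7.8 can assign closure to a patient who cannot meet the endpoint, and the plan gives no role to the wound status sought at withdrawal.

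A reader might infer that the rule mostly helps Restrata. The documents do not support that. It does so when exits are about equal between arms or concentrated in Restrata, and imputation is arm-specific. It works against Restrata when control exits exceed about twice Restrata exits, as they would if early exit tracks failure to heal. A model pooling the arms without a treatment term would give about no shift with equal exits.

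Nor should the 20% loss allowance in 7.3 be read as 20% known failures. It covers loss to follow-up, where outcomes are mostly unknown.

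Under the assumed exit rates, the size ranges from negligible (one exit per arm, 1.7 points) to enough to decide the result (four per arm, 33.3 against 40.0 points, with p = 0.052 under the stricter coding). Clear inflation of the one-sided 5% error, to about 10–11%, needs such exits concentrated in Restrata.

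**What to change.** In section 7.8, before the interim analysis:

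1. Count death, or amputation of all or part of the study limb, before confirmed closure as not closed in the primary analysis. Where an amputation spares the ulcer this is a convention, but participation ends there and closure cannot be confirmed.
2. Impute only patients whose 12-week status is unknown. Put the wound status recorded at withdrawal and the last measured wound area in the imputation model, and state whether the model is fitted by arm.
3. Add a sensitivity analysis counting all missing patients as not closed.
4. Apply the same coding to the conditional power calculation in 7.4.

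The cost is analysis-plan wording. Reported closure rates may be slightly lower; the treatment difference may move either way.
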